4.5 Analysis Sets

All enrolled patients: all patients who signed the informed consent form.

Full Analysis Set (FAS): all patients who were scheduled to receive the rhPSMA-7.3 (¹⁸F) injection having met the inclusion/exclusion criteria or have received rhPSMA-73 (¹⁸F) injection.

Full Safety Population (FSP): all patients who received the rhPSMA-7.3 (¹⁸F) injection.

Efficacy Analysis Population (EAP): all patients who received rhPSMA-7.3 (¹⁸F) injection followed by a PET/CT scan and for whom sufficient data are available to permit a clear classification following the SoT algorithm.

Per Protocol Population (PP): All evaluable patients in the EAP population without major protocol deviations which could affect the primary endpoint.

Evaluable PET Scan Population (EPSP): All patients who received the rhPSMA-7.3 (¹⁸F) injection with a PET scan.

All safety analyses will be performed using the FSP. The primary analysis of CDR and PPV will be based on the EAP.

A summary of patients in each population will be given, including a breakdown of populations by center.

Upon database release, protocol deviation and analysis set outputs will be produced and will be sent to BED for review. An analysis set classification meeting will be arranged to discuss the outputs and to decide which subjects and/or subject data will be excluded from certain analyses. Decisions made regarding the exclusion of subjects and/or subject data from analyses, and the agreement of population inclusion for each patient, will be made prior to locking the database and will be documented and approved by BED.

A summary of the number and percentage of subjects entering and completing each phase of the study for each analysis set will be provided. Analysis set used: FAS.

A by-subject listing of analysis set details will be provided. This listing will include center, subject identifier, and inclusion/exclusion flag for each set and reason for exclusion from each set. All

Parexel International

Blue Earth Diagnostics Ltd
BED-PSMA-302

Statistical Analysis Plan

subjects screened appear on this listing. If subject data has been partially excluded, visit will also appear on this listing.

4.6 Demographic and Other Baseline Characteristics

The demographics and baseline characteristics will be summarized using the FAS.

The following summaries will be provided:

- Demographics: age at informed consent (including age groups of <65, \geq 65 and the subgroup of \geq 75), sex, ethnicity, race and height. Weight at screening and weight and Body Mass Index (BMI) on Day 1 will be in the summary.
 - BMI will be calculated as $BMI(kg/m^2) = \frac{weight(kg)}{height(m)^2}$
- History of current disease:
 - Time (months) from initial diagnosis of prostate cancer to informed consent Time (months) since diagnosis of biochemical recurrence.
 - Time (months) since Start date of prior curative intent treatment with or without adjuvant therapy
 - Time (months) since End date of prior curative intent treatment with or without adjuvant therapy
 - Duration (months) of prior curative intent treatment with or without adjuvant therapy
 - For each of these durations, Dates with missing day will be imputed with 15th, dates with missing month and day will be imputed with 01 Jul to obtain the duration. If this results in a negative duration, duration will be missing.
 - A month is assumed to take 30.4375 days.
- Medical history

By subject listings of demographics and baseline characteristics will be provided

4.7 Patient management plans

Patient intended treatment at baseline (before rhPSMA-7.3 (¹⁸F) PET imaging) and post rhPSMA-7.3 (¹⁸F) PET imaging will be listed by subject and time point. The listing will show planned treatments and include details on therapy as applicable, by Subject, Center and Visit. A summary of planned treatment at baseline and post PET imaging (but before confirmatory imaging) by Center and overall will be provided using the FAS.

The options in the intended management plan are:

- Watchful Waiting / Active Surveillance
- Androgen-Deprivation Therapy
- Radiotherapy
- Cryotherapy
- Brachytherapy
- HIFU
- Prostatectomy
- Lymph Node dissection

Parexel International

Blue Earth Diagnostics Ltd
BED-PSMA-302

Statistical Analysis Plan

- Other

The options in the revised management plan are:

- Watchful Waiting / Active Surveillance
- Androgen-Deprivation Therapy
- Radiotherapy
- Cryotherapy
- Brachytherapy
- HIFU
- Prostatectomy
- Targeted treatment of PSMA positive extra-pelvic / bony areas
- Chemotherapy / Immunotherapy
- Lymph Node dissection
- Other

The intended management plan and revised management plan will be compared, and assigned to one of the following categories, for each patient:

- No Change
- Major Change
- Other Change
- Additional Information Required
- Intended Plan Not Valid

The assignment of the category and sub-category in change in management plan to each subject will be performed manually by Blue Earth Diagnostics team, using the SDTM data on the intended and revised management plans provided by Parexel as the source data. An Excel file containing the unique subject ID, category and sub-category in change in management plan.

Patients who have intended management plan but no revised management plan will be considered as having no change in management plan. This is because the question “Is the management plan revised after PSMA scan results available:” is ambiguous – when the site selects “no” as the answer, it is unclear whether this means there is no revision to the management plan, or the management plan after PSMA scan results is not available.

The use of the phrase “revised management plan” for the management plan after the PSMA scan results can be confusing also, because the management plan is not “revised” as such if it is the same as the intended management plan. Therefore the “intended management plan” and the “revised management plan” will be reworded to “pre-PSMA management plan” and “post-PSMA management plan”, to clearly indicate that the analysis is to compare the management plans before and after PSMA respectively.

The pre-PSMA management plan and post-PSMA management plan will be compared, and assigned to one of the following categories in Table 2, for each patient with both pre-PSMA and post-PSMA plans.

Parexel International

Blue Earth Diagnostics Ltd

BED-PSMA-302

Statistical Analysis Plan

Table 2: Changes in Management Plan

Change in Management Plan Category	Definition
No Change	
When there is no change from the pre-PSMA management plan to the post-PSMA management plan, because:
 
 • The options selected in the pre-PSMA management plan are equivalent to the options selected in the post-PSMA management plan, or • There is a pre-PSMA management plan, and the post-PSMA management plan leading question “Is the management plan revised after PSMA scan results available:” is answered as “no”, or there is no post-PSMA management plan.
Major Change	
When the main options in the pre-PSMA management plan are different from the main options selected in the post-PSMA management plan, and the post-PSMA management plan is clearly a treatment plan.

Minor Change	
When the main options in the pre-PSMA management plan and post-PSMA management plan are the same, but there are some differences in the details (e.g. different radiation fields for radiotherapy)

Additional Information Required	
When the main options in the pre-PSMA management plan are different from the main options selected in the post-PSMA management plan, but the post-PSMA management plan indicates additional diagnostic procedures to be performed (e.g. MRI or biopsy before a decision on treatment plan is taken), or the post-PSMA management plan does not contain clear choice of treatment plan.

Intended Plan Not Valid	
When the pre-PSMA plan does not contain sufficient or clear information on the treatment plan prior to PSMA, or the pre-PSMA plan date is after day 1 (PSMA administration date)

The subcategories in “major change” will be assigned manually using Table 3.

Table 3: Subcategories for Major Change

“Major Change” Subcategories	Definition of the subcategory
Salvage or non-curative systemic therapy to watchful waiting	
Pre-PSMA Management Plan: Any categories other than “Watchful Waiting / Active Surveillance”
 
Post-PSMA Management Plan: “Watchful Waiting / Active Surveillance” only

Parexel International

Blue Earth Diagnostics Ltd
BED-PSMA-302

Statistical Analysis Plan

“Major Change” Subcategories	Definition of the subcategory
Salvage therapy to non-curative systemic therapy	Pre-PSMA Management Plan: Any categories other than “Watchful Waiting / Active Surveillance”, “Androgen-Deprivation Therapy”, “Chemotherapy / Immunotherapy” or any other therapies which are not considered as non-curative systemic therapy Post-PSMA Management Plan: “Androgen-Deprivation Therapy” or “chemotherapy/immunotherapy” or any other therapies which are considered as non-curative systemic therapy
Watchful Waiting to Salvage or non-curative therapy	Pre-PSMA Management Plan: “Watchful Waiting / Active Surveillance” only post-PSMA Management Plan: Any categories other than “Watchful Waiting / Active Surveillance”
Alternative major change	Major change that does not meet the definition of the above subcategories.

“Minor change” is defined as a change in therapy within the same category from the pre-PSMA management plan to the post-PSMA management plan. The following subcategories in “minor change” will be assigned manually upon review of the data using Table 4

Table 4: Subcategories for Minor Change

“Minor Change” Subcategories	Definition of the subcategory
Modified RT field plan	Pre-PSMA Management Plan and post-PSMA Management Plan both contain Radiotherapy (may include other therapy/therapies, as long as there is no change in these therapies)
Modified Androgen-Deprivation Therapy Regimen	Pre-PSMA Management Plan and post-PSMA Management Plan both contain Androgen-Deprivation Therapy only
Alternative other change	Pre-PSMA Management Plan and post-PSMA Management Plan have the same category / categories selected, but the details within the categories have changed.

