Study Title	A prospective, Phase 3, multi-center, single-arm, imaging study investigating the safety and diagnostic performance of rhPSMA-7.3 (¹⁸ F) PET ligand in men with suspected prostate cancer recurrence based on elevated PSA following prior therapy
Protocol Number	BED-PSMA-302
Phase	3
Sponsor	Blue Earth Diagnostics
Funding Organization	Blue Earth Diagnostics Ltd

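### SAP 4.7 has the sponsor's team classify every patient's management change by hand, with no stated masking or completion date, although many of the rules could be programmed

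*SAP*

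**What the plan says.** The investigator records an intended plan before the scan and a further plan after it (Protocol 9.2.4). SAP 4.7 gives nine options on the first form and eleven on the second. Table 2 then sorts patients into No Change, Major Change, Minor Change, Additional Information Required or Intended Plan Not Valid. Tables 3 and 4 subdivide Major and Minor Change.

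On who does the sorting, SAP 4.7 says: "The assignment of the category and sub-category in change in management plan to each subject will be performed manually by Blue Earth Diagnostics team". They work "using the SDTM data on the intended and revised management plans provided by Parexel as the source data" and return an Excel file. The Major Change subcategories "will be assigned manually using Table 3"; the Minor Change subcategories "will be assigned manually upon review of the data using Table 4". The Protocol synopsis names the same company as sponsor and funder ("Blue Earth Diagnostics Ltd").

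The result is reported as a frequency and proportion with a 95% CI (SAP 4.16.3.5). Secondary endpoints are descriptive (Protocol 16.5).

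**The concern.** This endpoint describes whether the scan alters care. The party with an interest in the answer scores each patient, and SAP 4.7 states neither masking to PET or SoT results nor a point by which scoring must be complete. The same SAP protects judgement elsewhere: PET scans go to three blinded independent readers, imaging SoT goes to different readers (3.2.2.3), and analysis-set decisions must be made and documented before database lock (4.5). The independent checking in SAP 4.1 covers tables, figures and listings. It is output quality control and does not check the classification.

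At stake is the credibility of the reported percentage of patients with changed management. Its confidence interval reflects sampling error only, so any systematic tilt in scoring would not show.

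**Working it through.** The plan states no expected change rate or precision for this endpoint, so there is no figure to reproduce. The check has two parts.

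**1. Which rules need judgement?** Reading Tables 2 to 4 rule by rule:

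| Rule | Acts on recorded fields | Needs judgement |
|---|---|---|
| No Change | Comparison of options ("The options selected in the pre-PSMA management plan are equivalent to the options selected in the post-PSMA management plan"); leading question answered no; no post-scan plan | Whether a post-only option is 'equivalent' to a pre-scan one |
| Major Change | Difference in options | 'Main options' undefined; "and the post-PSMA management plan is clearly a treatment plan" undefined |
| Additional Information Required | Difference in options | Whether the post-scan plan makes a 'clear choice' |
| Intended Plan Not Valid | Pre-scan plan dated after the day of administration | 'Sufficient or clear' information undefined |
| Minor Change | Same options | Differences in plan details |
| Table 3, four rows | Three rows name options; the fourth is the remainder | Open clause for other non-curative systemic therapies |
| Table 4, three rows | Two rows name an option | Whether the details differ |

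Two features follow.

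- Major Change and Additional Information Required start from the same condition, differing main options. Only the undefined word 'clear' separates them.
- Two of the eleven post-scan options, targeted treatment of PSMA-positive areas and chemotherapy/immunotherapy, are absent from the nine pre-scan options, and no mapping is given. A patient moving from radiotherapy to targeted treatment could be read as a different option or as the same option with different detail.

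**2. How much could discretion move the result?** The number of borderline patients is not given, so this is sensitivity and not an estimate of bias. Assume n = 300 classifiable patients and a Major Change rate p = 0.40; neither is in the documents.

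- Standard error = √(p(1−p)/n) = √(0.40 × 0.60 / 300) = 0.0283, or 2.8 points.
- 95% half-width = 1.96 × 2.83 = 5.5 points.
- Moving 5% of patients, 15 of 300, in one direction shifts the percentage by 15/300 = 5.0 points.

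Each 1% of patients moved one way shifts the result by 1 point. Exact (Clopper-Pearson) half-widths over a range of assumed rates, with the planned 316 patients and the planned 190 positive cases as denominators:

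| Assumed rate | n = 316: half-width (patients) | n = 190: half-width (patients) |
|---|---|---|
| 20% | 4.6 points (14) | 5.9 points (11) |
| 35% | 5.4 points (17) | 7.0 points (13) |
| 50% | 5.7 points (18) | 7.3 points (14) |

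A net one-directional move of about 5% to 7% of patients therefore matches the half-width.

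The denominator may move too, because the SAP does not say whether Intended Plan Not Valid patients stay in it. With an assumed 110 changed patients of 316, the rate is 110/316 = 34.8%. If 32 others are classed not valid and dropped, it is 110/(316 − 32) = 110/284 = 38.7%.

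**The case against.** The case for leaving SAP 4.7 alone has real substance.

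- Where ticked options fix a row, a manual coder has little latitude. This stands, and it places the risk in the judgement terms. It also means that programming alone would not remove the risk.
- The named source data are the two plans; PET and SoT results are not listed as inputs. This is true, but it is not a statement of masking.
- Some rules work against inflation. A missing post-scan plan counts as No Change, and a differing plan without a clear treatment choice is kept out of Major Change. Both stand, but neither constrains who decides what is clear.
- The endpoint covers major and other changes. A patient moved from Minor to Major alters the split and leaves total change the same. This stands.

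A reader might also infer three stronger points that the documents do not support.

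- That visible plan order is a defect, to be cured by showing the plans unlabelled in random order. Order is built into the definitions: Table 2 tests the post-scan plan for clarity and the pre-scan plan for validity and date, and three Table 3 rows are directional. The two post-only options would reveal it anyway.
- That the result cannot be reproduced. SAP 4.7 provides a by-subject listing of both plans, and the rules are written down, so re-scoring is possible within the limits of the undefined terms.
- That the illustrated shift exceeds sampling error. It exceeds one standard error (5.0 against 2.8 points) but not the 95% half-width (5.5 points) at the same inputs.

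**Conclusion.** The point holds as a risk of classification bias. SAP 4.7 gives the sponsor's team case-by-case assignment for every subject, states no masking to PET or SoT results, and sets no requirement to finish before results are known. Many of the rules could be applied without judgement. The discretion that matters sits at the Major Change, Additional Information Required and Intended Plan Not Valid boundaries and in matching the two option lists.

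The size is conditional. At an assumed 300 patients and 40%, a 5% one-directional reclassification moves the Major Change percentage 5 points, close to the 95% half-width of about 5.5 points. How many patients are borderline, and whether they would all move one way, is unknown.

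A reader might infer that the percentage will be inflated or that study success is in doubt. The documents show neither. The endpoint is descriptive, without threshold or alpha, and success rests only on CDR and PPV. The change is worth making because it is cheap and specific.

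**What to change.** Amend SAP 4.7 as follows.

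1. Define 'main options' and what makes a plan 'clear' or 'sufficient', and list which therapies fall under the open clause in Table 3.
2. Prespecify a mapping between the nine pre-scan and eleven post-scan options.
3. Have the CRO program the option-equality, leading-question and plan-date rules, and the option-based conditions in Tables 3 and 4.
4. Limit manual review to free-text and plan-detail cases. Existing staff can do it, masked to central PET and SoT results, with decisions finished and documented before database lock, as SAP 4.5 already requires for analysis sets.
5. State whether Intended Plan Not Valid patients stay in the denominator.
6. Report the number of patients set manually and a sensitivity result from the programmed rules alone.

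Two inconsistencies should be reconciled in the same edit. The category list in 4.7 and the analysis in 4.16.3.5 refer to other changes, while Table 2 uses Minor Change. Section 4.16.3.5 requires documented plans before and after the scan, while 4.7 counts a missing post-scan plan as No Change.

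The cost is SAP wording, a short derivation program and some review time. No mandatory second reviewer is needed.

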4.8 Medication and Prostate Cancer Surgical Procedure history

Medication and/or procedure start and stop dates will be compared to the date of IP administration to allow medications/procedures to be classified as either Prior only, both Prior and Concomitant, or

Parexel International

Blue Earth Diagnostics Ltd
BED-PSMA-302

Statistical Analysis Plan

Concomitant only. Medications and/or procedures starting after the completion/withdrawal date will be listed but will not be classified or summarized.

Medications/procedures that start and stop prior to the date of dose of IP administration will be classified as Prior only. If a medication/procedure starts before the date of IP administration and stops on or after the date of IP administration, then the medication/procedure will be classified as both Prior and Concomitant. Medications/procedures will be classified as Concomitant only if they have a start date on or after the date of first dose of study medication.

If medication/procedure start and/or stop dates are missing or partial, the dates will be compared as far as possible with the date of IP administration. Medications/procedures will be assumed to be Concomitant only, unless there is clear evidence (through comparison of partial dates) to suggest that the medication/procedure started prior to the IP administration. If there is clear evidence to suggest that the medication/procedure started prior to the IP administration, the medication/procedure will be assumed to be both Prior and Concomitant, unless there is clear evidence to suggest that the medication/procedure stopped prior to the IP administration. If there is clear evidence to suggest that the medication/procedure stopped prior to the IP administration, the medication will be assumed to be Prior only.

Medications will be coded using WHODrug Global Dictionary and summarized by ATC code (levels 2 and 4) and Preferred term and listed by subject using the FAS. In case of missing level 4 coding the level 3 coding will be used.

Medications for prostate cancer will be summarized and listed separately.

Procedures will be summarized by System Organ Class (SOC) and Preferred Term (PT) using MedDRA dictionary and listed by subject.

For some endpoints subjects with Radical Prostatectomy (RP) and Prior Radiotherapy (RT) will be selected. The identification of subjects with RP or RT will be derived from the Procedures (PR) eCRF page:

- A subject is considered to have had RP if PT contains the phrase “Radical prostatectomy” or “Prostatectomy”.
- A subject is considered to have had RT if PT contains the phrase “Radiotherapy”, or equal to “Brachytherapy” or “Brachytherapy to prostate”

Concomitant medication will be coded using WHODrug Global (WHODD) WHODD_Global_01Sep2019_B3.

Procedures will be coded using Medical Dictionary for Regulatory Activities (MedDRA) 22.1.

All summaries will be performed using the FSP

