4.10 PSA

PSA will be analyzed using the FAS.

Most recent PSA level will be summarized as a continuous variable.

An additional summary of PSA level will be by prior therapy based on PT. Each patient will be in one category only.

- Prior Prostatectomy (as defined in section 4.8). This includes all patients who had other therapies (including radiotherapy), as long as they had prostatectomy.
- Prior Radiation Therapy (as defined in section 4.8). This excludes patients with previous prostatectomy.
- Other: Neither Radiation Therapy nor Prostatectomy.

A plot (spaghetti plot) showing subject PSA against Study Day (relative to PET scan) by center. PSA will be listed by patient date, and study day, with a cut-off of two years (day -730).

In addition, PSA will be categorized using the categories: $PSA < 0.5$, $0.5 \leq PSA < 1.0$, $1.0 \leq PSA < 2.0$, $2.0 \leq PSA < 5.0$, $5.0 \leq PSA < 10.0$, $10.0 \geq PSA$ (ng/mL). A frequency table of the categories with proportion will be provided overall. These same categories will be used for analysis of subgroups on PSA level. In case of categories with low counts a category may be merged with an adjacent category in order to have at least five patients in each category.

The PSA doubling time will be calculated by first doing regression of historical natural log PSA on date of PSA measurement and subsequently division of natural log 2 (0.693) by the slope, using the last 3 values in the 2 years prior to PSMA dosing in the model. A month is assumed to take 30.5 days. In case there are not 3 acceptable measurements in the prior 2 years then no doubling time will be provided. Negative slopes will be missing in summaries.

Parexel International

Blue Earth Diagnostics Ltd
BED-PSMA-302

Statistical Analysis Plan

In case of incomplete dates for PSA measurement, for the doubling time calculation the date may be imputed or the measurement may be ignored, based on the following rules:

- If the day part is missing but the month and year are known, then the 15th of the month will be used.
- If the day and month parts are missing, then the PSA measurement will be ignored.

In case of less than PSA values (e.g. '<0.1') the numerical value will be used after removal of the '<' character.

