4.16.4.5 Patient and regional level detection rates of rhPSMA-7.3 (¹⁸F) PET as a function of PSA, prior Gleason score and PSAdt in a) post-RP; b) post-RT patients.

This concerns patients in subgroups of the EPSP with an extra subgroup condition, for a) the patient has had RP, for b) the patient has had RT (see Section 4.8). The regions analysis will concern local

Parexel International

Blue Earth Diagnostics Ltd
BED-PSMA-302

Statistical Analysis Plan

recurrence, pelvic lymph nodes and other. Patients will be analyzed by PSA category (Section 4.10), by total (biopsy and surgery) Gleason score (Section 4.9) and by PSAdt category (Section 4.10) for each of the blinded readers and their majority.

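### SAP 4.8 aims to select radical prostatectomy and prior radiotherapy, but its two text-match bullets limit neither procedure type nor date, so some patients can fall into the wrong exploratory group

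*SAP*

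**What the plan says.** SAP 4.8 states the purpose first: "For some endpoints subjects with Radical Prostatectomy (RP) and Prior Radiotherapy (RT) will be selected". It then names the source: "The identification of subjects with RP or RT will be derived from the Procedures (PR) eCRF page". Two bullets set the flags:

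- RP: "A subject is considered to have had RP if PT contains the phrase “Radical prostatectomy” or “Prostatectomy".
- RT: "A subject is considered to have had RT if PT contains the phrase “Radiotherapy”, or equal to “Brachytherapy” or “Brachytherapy to prostate".

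Earlier in the same section, procedures are dated against administration of the investigational product. "Medications/procedures that start and stop prior to the date of dose of IP administration will be classified as Prior only"; those that straddle the date are both Prior and Concomitant. At the other end, "Medications/procedures will be classified as Concomitant only if they have a start date on or after the date of first dose of study medication". A procedure with a missing or partial date is taken as Concomitant only, unless the partial date clearly shows an earlier start. The two bullets do not cite this classification.

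The flags are used in three places:

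- **SAP 4.10**, PSA by prior therapy, one category per patient. The first category is "Prior Prostatectomy (as defined in section 4.8") and it takes precedence. The radiation category leaves out anyone with a previous prostatectomy.
- **SAP 4.16.4.3**, exploratory endpoint 3 (upstaging). The groups are RP with or without RT, RT without RP, and other therapies.
- **SAP 4.16.4.5**, exploratory endpoint 5 (detection by PSA, Gleason score and PSA doubling time): "for a) the patient has had RP, for b) the patient has had RT (see Section 4.8"). These two groups are not made exclusive.

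**The concern.** The aim and the operative rule differ in two ways. The aim says radical prostatectomy, but the second phrase of the RP bullet accepts a prostatectomy term without that word. The aim says prior radiotherapy, but the RT bullet has no date, and the RP bullet has neither a date nor the word prior in its lead-in. A programmer who codes the bullets as they stand would not carry out the stated aim.

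Misplaced patients would differ systematically from the group they join. Under Protocol 6.2, primary-radiotherapy patients enter at nadir +2 ng/mL, so at a PSA of at least 2, while post-RP patients can enter from 0.2 ng/mL. Protocol 1.2 reports detection of 58%, 83% and 97% at PSA below 1, 1 to below 2, and 2 or above. Treatment given after the scan may also depend on the scan, so letting it set a flag would allow the index test to influence group membership.

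**Working it through.** The plan gives no figure for this point, so the check is of logic. The two bullets were coded as string matches and applied to invented histories, first with no date condition and then counting only procedures before administration. The terms are test strings, not trial data, and the documents do not show which coded terms will occur.

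| History (test terms) | Bullets as written | With the date condition |
|---|---|---|
| 1. Primary RT; earlier non-radical procedure coded *Prostatectomy* | RP in 4.10 and 4.16.4.3; both groups in 4.16.4.5 | No change |
| 2. Primary RT; earlier *Transurethral prostatectomy* | As row 1 if case is ignored; RT throughout if case is respected | No change |
| 3. RP; *Radiotherapy* after PET | RP in 4.10 and 4.16.4.3; both groups in 4.16.4.5 | RP throughout |
| 4. Focal therapy; *Radiotherapy* after PET | RT throughout | Other in 4.10 and 4.16.4.3; neither group in 4.16.4.5 |
| 5. Primary RT; *Radical prostatectomy* after PET | RP in 4.10 and 4.16.4.3; both groups in 4.16.4.5 | RT throughout |
| 6. RP; *Radiotherapy to bone* before PET | RP in 4.10 and 4.16.4.3; both groups in 4.16.4.5 | No change |

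**Procedure type (rows 1 and 2).** A date condition does not help; only a limit on procedure type does. Row 2 also shows that the result depends on case handling, which the SAP does not state.

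**Date (rows 3 to 5).** The date condition removes all three. In row 3 the only change is entry to the 4.16.4.5 RT group; the patient never leaves RP.

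**Site (row 6).** Only 4.16.4.5 changes, and only if such a record is on the page.

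**Adding the word prior is not enough.** Under 4.8, a historical RP or RT with no date defaults to Concomitant only. Filtering on the Prior class would then remove a correct flag.

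**Illustration of size for row 1.** These counts are assumptions. Take 316 patients: 79 with primary RT, all at PSA 2 or above, and 237 post-RP, split 126, 55 and 56 over the three PSA bands.

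- Post-RP detection without misplacement: (126 × 0.58 + 55 × 0.83 + 56 × 0.97) / 237 = 173.05 / 237 = 73.0%.
- If 4 RT patients (5% of 79) move in at 97%: (173.05 + 3.88) / 241 = 73.4%.
- If 16 (20%) move in: (173.05 + 15.52) / 253 = 74.5%.

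The pooled rate rises by 0.4 to 1.5 points. Misplaced patients would make up 4/60 = 7% to 16/72 = 22% of the post-RP stratum at PSA 2 or above. The detection rate in that stratum does not move, because both sources are given 97%. Any shift would therefore appear in the Gleason and doubling-time breakdowns, which pool over PSA.

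**The case against.** The strongest reply is that the bullets should be read in context. The lead-in says prior radiotherapy, the section title speaks of prostate cancer surgical procedure history, and 4.10 labels both of its groups as prior. On that reading, rows 3 to 5 are drafting gaps and not the plan's intent. That stands. A reader might infer that the SAP means post-scan radiotherapy to define a post-RT patient, and the documents do not support this. They also do not show that salvage treatment reaches the Procedures page: it has its own row in Protocol Appendix 1, and the eCRF page is not named. What remains is that 4.16.4.3 and 4.16.4.5 refer back to 4.8 and ask only whether the patient has had RP or RT.

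A second reply is that the RP bullet does not certainly capture transurethral or simple prostatectomy. That also stands. A case-sensitive match misses a qualified lower-case term, and coding practice is not in the documents. Accepting a bare *Prostatectomy* term may be a sensible way to keep true RP patients, since radical prostatectomy is the only prostatectomy among the qualifying treatments in Protocol 6.2. But the rule has no step to tell the two apart.

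Third, the section title may keep radiotherapy for other conditions off the page, which weakens the site point.

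Finally, a reader might infer that the RT group loses patients in every analysis. It does so only in 4.10 and 4.16.4.3; in 4.16.4.5 they stay in RT and are also counted in RP.

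**Conclusion.** The point holds as a gap between stated aim and operative rule. The procedure-type part is the firmer one: a bare prostatectomy term for a non-radical procedure puts a primary-radiotherapy patient in RP under every variant tested, with or without a date condition. The date part is conditional on post-scan procedures being on the Procedures page and on the bullets being applied without their lead-in.

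The number of patients affected cannot be derived from the documents. The 0.4 to 1.5 point illustration rests wholly on assumed counts and indicates only that the pooled effect would probably be small. The reach is limited to the PSA summary by prior therapy and exploratory endpoints 3 and 5, which Protocol 16.5 treats descriptively. A reader should not infer any effect on CDR, PPV, power or the success rule, because none of them uses these flags.

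**What to change.** Amend the two bullets in SAP 4.8 as follows:

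- Only procedures for prostate cancer that started before rhPSMA-7.3 administration set either flag.
- The qualifying preferred terms for RP and RT are listed, with case-insensitive matching, after a review of all matched terms before database lock.
- A bare *Prostatectomy* term counts as RP only when the record shows that it was the radical, curative-intent procedure. Transurethral and simple prostatectomy do not count.
- A historical RP or RT with a missing date is resolved at that review and is not defaulted to Concomitant only.

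Taking the flags instead from the prior curative-intent treatment record in SAP 4.6 is tempting, but not established as workable: 4.6 shows dates and does not show treatment type. Its dates may help to settle individual cases at the review.

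The cost is SAP wording and a short term review, which could be done alongside the pre-lock data review meeting in SAP 4.4.2. No new data collection is proposed.
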